4.7 Reported device issues

Device issues as reported or interpreted by the clinical site are captured in the eCRF. These reported device issues will be evaluated and adjudicated by Luminicell personnel for impact to subject safety, impact to data capture, and categorization. Issues that resulted in an impact to data capture may be removed from the efficacy analysis. The 'Device Issues' external data set will be used for analysis and not generated by the device issues reported in the eCRF.

4.8 General considerations

All analyses will be performed under Good Clinical Practice (GCP) standards using the statistical analysis plan establish in this document. All analyses will be conducted, and tables and listings generated using Statistical Analysis System (SAS®) Version 9.4 or higher. Graphics may be prepared with SAS Version 9.4 or higher; R version 3.6.1 or higher (R Core Team (2019)), SigmaPlot 12.3 or higher (Systat Software, Inc., San Jose, California). Subject level data will be provided as a listing to support tables and figures. Summaries will be provided overall, by device size, and by site.

4.8.1 Numerical precision

For reporting of descriptive statistics, the mean, SD, median, min, max and quantile will be presented to 1-digit precision. The minimum, median, and maximum will be presented to the same precision as the source data. The maximum number of decimals will be two, no matter how precise the source data is. The percentages will be reported to 1 decimal (format of xx.x%). Sensitivity and specificity will be reported as percentages with 1-digit precision (format of xx.x%). P-values will be reported to three (3) decimal places or as < 0.001.

4.8.2 Multiple images to cover entire shave or multiple shaves for one image

To accurately evaluate the study endpoints, it is critical that images are collected from the entire lumpectomy cavity surface. To achieve this, multiple images may be required to record the LUM assessment for an entire orientation (e.g. 2 images to cover the entire superior orientation) but a single shave may exist. When multiple images exist for a given orientation or shave, the combination of the images will be considered as one single output as described below:

- All images for a given orientation or shaved region are LUM negative, then the LUM result for the entire orientation or shaved region is considered as LUM negative.

LUMICELL CONFIDENTIAL

This document is confidential. Do not disclose or use except as authorized.

- If one or more of the images for a given orientation or shaved region is LUM positive, then the LUM result for the entire orientation or shaved region is considered as LUM positive.

When there are more than one shave for a single image, the pathology finding for the combination of the shaves will be considered as one as follows:

- If no tumor is found on the shaves, then the combination of the shaves is considered as truth standard negative.
- If any of the shaves has tumor, then the combination of the shaves is considered as truth standard positive.

4.8.3 Missing and spurious data

During Luminicell-guided imaging, when there is not enough tissue to be removed (e.g. too close to skin or too close to the chest wall) no LUM image shall be recorded because it does not generate an actionable result.

In the case where the LUM Imaging System indicates that a therapeutic shave needs to be removed but the surgeon decides not to follow this guidance, the reason for not doing so will be recorded in the patient's CRF or during imaging. These instances are considered as a protocol deviation. There are other cases when the shavings reach protocol limits so no shaving will be performed. In these cases, the data will be included in the performance evaluation as is - that is no Luminicell-guided shave-taken will be considered as no removing of cancer or positive margin. However, they will be considered as a detection if there are cancer in the re-excision or if there are positive margins on the corresponding orientations.

Occasionally, a cavity image may be recorded from an unintended region or the image may be deemed as low quality (blurry, out of focus, etc.). For example, the surgeon realizes that he/she placed the device in the wrong location within the cavity after recording an image. Since the LUM software does not allow to overwrite saved images, this situation will be documented, the image will be labeled as "image retaken", "eval", "initialscan" or "transient" and the image will be excluded from the analysis. In addition, images labeled as "lens issue" will be considered as a device malfunction and will be excluded from the analysis.

Other cases are handled as follows:

- When a patient was prescribed Letrozole adjuvant therapy prior to surgery, the patient will be removed from the device performance evaluation.
- When the time from injection of LUM015 to lumpectomy incision is greater than 6 hours due to unplanned surgical delays, the patients will be removed from the device performance evaluation.
- For the re-excision rate endpoints, all patients undergoing a re-excision will be included in the analysis.
- When an image is indicated negative by LUM Imaging System but the shave is taken due to X-ray or pathology suggestion, it will be kept for sensitivity and specificity evaluation, however, for the analysis related to margins, it is conditional and described in g.

LUMICELL CONFIDENTIAL

This document is confidential. Do not disclose or use except as authorized.

- e. In the case of a therapeutic shave taken but no image saved before the shave was removed, the shave will be excluded from analysis.
- f. In the case of the subject with minor deviation, like no blood drawn, high blood pressure, etc., data will be kept for device performance evaluation.
- g. In the case of SOC shave is taken after use of the Luminicell imaging system, if there is an image for this shave, it will be kept for sensitivity and specificity analysis. If there is a therapeutic shave ahead of the SOC shave but the orientation of the SOC shave is not the same as that of the therapeutic shave taken before it, this SOC shave will be kept for the margin analysis. If the orientation of the SOC shave is same as that of the therapeutic shave taken before it, this SOC shave should be removed from the margin analysis. If there is no therapeutic shave ahead of the SOC shave, this deviated SOC shave will be kept as SOC shave for margin analysis.
- h. In the case of a patient having bilateral lumpectomy, only the data collected from the trial side will be included in the device performance evaluation.
- i. In the case of multiple reports margins and tumors for one block of shave, the distance of the closest margin will be used and ‘Yes’ for the shave containing tumor if at least one report for that block is ‘Yes’.
- j. In the case of the unknown dimension of the shaves or 999 for any of the dimensions, the volume of the shave is the average of that of all the existing shaves of the corresponding type (SOC or Therapeutic).
- k. In the case of a tissue has unknown or unreported distances to margins, the data in the eCRF will indicate “unknown”, it will be interpreted as no specified distance has been reported or the options in the eCRF do not fit the distance description in the pathology report and/or the pathology worksheet. However, the determination for positive or negative margins in the corresponding orientations will depend the pathology determination on whether margins are positive or negative. For example, a pathology report may state “closest margin to invasive cancer is 1mm in medial”. Thus it is assumed that the margins for the other orientations are > 1mm but the specific distance is not reported. For orientations other than medial, the eCRF may indicate “unknown” for margin distance, but the margin status will be considered as “negative” for data analysis.
- l. For reported microinvasive cancer, adjudicated correction will be provided external to the eCRF and will be used to change the margin type from Invasive to DCIS following NCCN guidelines.
- m. Margins for SOC and final margins will be derived from the tumor distance to margins. If there is a discrepancy between the derived margins based on distance and the margin status determined by the clinical site (could be due to different criteria used by the clinical sites), adjudication of the margin status will be done by Luminicell based protocol defined margin criteria (section 3.1).

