#### 5.4.5 Other general procedures and injection of LUM015

For subjects with non-palpable tumors, an ultrasound, mammogram or MRI-guided localization procedure may be performed prior to or the same day as the surgery. Also, patients having a sentinel lymph node (SLN) mapping procedure may be injected with the radio-tracer Technetium-99 (Tc-99) per standard of care. LUM015 may be injected before or after any of these procedures, as long as it is injected  $4 \pm 2$  hours prior to surgery.

Prior to the surgery, the LUM Imaging Device of the size selected by the surgeon will be positioned in the operating room and an initialization procedure will be conducted to ensure that the performance parameters of the device are within defined specifications. If during the initialization

LUMICELL CONFIDENTIAL

This document is confidential. Do not disclose or use except as authorized.

procedures, the performance parameters are outside the defined specification, the user is prompted to discontinue use of the device. If the error cannot be fixed within a reasonable time in the operating room, these patients will receive standard of care treatment and will not be imaged with the LUM Imaging Device. These patients will be followed and monitored for safety the same way as those patients that undergo imaging with the LUM Imaging Device. The patients that are not imaged with the LUM Imaging Device will be included in the safety cohort but will not be part of the efficacy cohorts and will not be included in the total number of patients for training purposes. To avoid excessive tissue resection based on LUM015 signal during this investigational study, surgeons will take no more than 2 therapeutic shaves in a given orientation.

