3.3.2 Definition of truth standard for diagnostic performance

The instrument diagnostic accuracy is measured by sensitivity and specificity on a per-tissue basis. Because a LUM-guided shave does not exist when a negative LUM image is indicated we propose a hierarchical approach to determine the truth standard as depicted in Figure 2. The highest truth standard is whether pathology finds cancer in a tissue shave removed from the area that was imaged in the cavity. When a shave does not exist, then whether tumor is found in a re-excision surgery is considered as the truth standard. When neither a shave nor a second surgery exists for a given orientation that was imaged, the margin assessment of that orientation is used as truth standard. We believe that the hierarchical approach outlined to determine the truth standard is the most meaningful and practical assessment of device accuracy to predict the presence of cancer in the cavity.

LUMICELL CONFIDENTIAL

This document is confidential. Do not disclose or use except as authorized.

True positive = truth standard positive & Lum cavity image positive

False negative = truth standard positive & Lum cavity image negative

True negative = truth standard negative & Lum cavity image negative

False positive = truth standard negative & Lum cavity image positive

Figure 2: Definition of truth standard to evaluate the LUM Imaging System diagnostic performance.

When a therapeutic shave and re-excision are not available for an orientation, the margin from the prior resected tissue of the corresponding orientation will be used as ground inferred truth for evaluation (Figure 3).

The orientation of the tissue removed during a re-excision is typically noted in the pathology report and matches the orientation in which a positive margin was identified from the initial surgery. However, there will be instances in which the orientation of the tissue removed during a re-excision is not specified. In cases of unclear orientation of the tissue removed during re-excisions, it will be assumed that the re-excision was intended to address only the orientations with positive margins and pathology findings from the re-excision (tumor found/not found) will be applied to those orientations.

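### Read literally, SAP 4.8.3 conflicts with the SAP 3.3.2 truth hierarchy for unshaved LUM-positive orientations with a positive margin and a clean second surgery

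*SAP*

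**What the plan says.** **Truth hierarchy (SAP 3.3.2).** Pathology of a shave taken from the imaged area ranks first. Next: "When a shave does not exist, then whether tumor is found in a re-excision surgery is considered as the truth standard". The margin comes last: "When neither a shave nor a second surgery exists for a given orientation that was imaged, the margin assessment of that orientation is used" as the standard. The section foresees clean second surgeries at positive-margin sites. Where the orientation of re-excised tissue is unclear, the re-excision is assumed to address the positive-margin orientations, and "pathology findings from the re-excision (tumor found/not found) will be applied to those orientations". A mastectomy without cancer makes every orientation truth-negative, with no exception for orientations whose margin was positive.

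**Unshaved LUM-positive sites (SAP 4.8.3).** Two situations are covered. In one, the system "indicates that a therapeutic shave needs to be removed but the surgeon decides not to follow this guidance". In the other, the limit has been reached: "There are other cases when the shavings reach protocol limits so no shaving will be performed". The limit is in Protocol 5.4.5: "surgeons will take no more than 2 therapeutic shaves in a given orientation". For both, "the data will be included in the performance evaluation as is". They earn no credit for removing cancer or a positive margin, but "they will be considered as a detection if there are cancer in the re-excision or if there are positive margins on the corresponding orientations".

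The SAP has no corresponding rule for unshaved LUM-negative orientations, so these stay under 3.3.2.

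**The concern.** The two sections can give different truth labels to the same orientation. In 3.3.2 a clean second surgery displaces a positive margin. In 4.8.3 either finding is enough, and nothing confines the margin condition to patients without a second surgery.

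The difference goes one way. The 4.8.3 sentence applies only when LUM was positive. At an unshaved orientation with a positive margin and a clean second surgery, a positive call could be credited as a detection while a negative call is credited as a true negative. In a diagnostic 2x2 table the reference result must not depend on the result of the test being assessed.

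Two features make the combination worth settling in advance. Protocol 3.1 says positive margins call for a second procedure, and SAP 3.3.2 says re-excised tissue typically matches the positive-margin orientation, so the two conditions will often meet on the same tissue. The sites concerned are surgeon overrides and orientations at the shave limit, which are not a random subset.

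The SAP labels diagnostic performance a co-primary endpoint of the pivotal study, and Protocol 15.5 uses the combined Phase B and Phase C data to power that study. Two analysts who start from different sections could produce different tables.

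**Working it through.** **1. Classification.** For an unshaved orientation there are 2 LUM results × 3 second-surgery states × 2 margin states = 12 combinations. Each was classified by the 3.3.2 hierarchy and by 4.8.3 read literally, with the latter applied to LUM-positive sites only.

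| Second surgery | Margin | LUM+, 3.3.2 | LUM+, 4.8.3 literal | LUM−, 3.3.2 |
|---|---|---|---|---|
| Cancer | + | TP | TP | FN |
| Cancer | − | TP | TP | FN |
| **Clean** | **+** | **FP** | **TP** | **TN** |
| Clean | − | FP | FP | TN |
| None | + | TP | TP | FN |
| None | − | FP | FP | TN |

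One combination of the 12 differs.

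**2. Direction.** Let k be the number of orientations in that combination (k ≤ FP). The literal rule moves them from FP to TP:

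- Sensitivity goes from TP/(TP+FN) to (TP+k)/(TP+FN+k). It rises, or is unchanged if FN = 0.
- Specificity goes from TN/(TN+FP) to TN/(TN+FP−k). It rises, or is unchanged if TN = 0.
- The Youden Index is their sum minus 1, so it cannot fall.

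**3. Size.** The documents give no value of k and no expected 2x2 table, so there is no plan figure to reproduce here. The only anchor is Protocol 15.2: 19 + 32 = 51 pathology positives. All other counts below are assumptions.

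*Table A (assumed): 41 TP, 10 FN, 150 FP, 700 TN.*

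| k | Sensitivity | Specificity | Youden |
|---|---|---|---|
| 0 | 41/51 = 80.4% | 700/850 = 82.4% | 0.627 |
| 2 | 43/53 = 81.1% | 700/848 = 82.5% | 0.637 |
| 5 | 46/56 = 82.1% | 700/845 = 82.8% | 0.650 |
| 8 | 49/59 = 83.1% | 700/842 = 83.1% | 0.662 |

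*Table B (assumed): 47 TP, 4 FN, 60 FP, 240 TN.* Its sensitivity is near 93%, the value at which 51 positives give the roughly 7% margin of error in Protocol 15.2: 1.96 × √(0.93 × 0.07/51) = 0.070.

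| k | Sensitivity | Specificity | Youden |
|---|---|---|---|
| 0 | 47/51 = 92.2% | 240/300 = 80.0% | 0.722 |
| 5 | 52/56 = 92.9% | 240/295 = 81.4% | 0.742 |
| 10 | 57/61 = 93.4% | 240/290 = 82.8% | 0.762 |

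At k = 8 in Table A, sensitivity moves by 83.1 − 80.4 = 2.7 points.

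**The case against.** **The hierarchy may still govern.** SAP 3.3.1 says sensitivity, specificity and the Youden Index use the hierarchical truth standard. SAP 4.8.3 names the second and third levels of that hierarchy in the same order and does not say the order is suspended. Its term for the credited outcome, a detection, is undefined and is not one of the four cells of SAP Table 1. The sentence may be shorthand for the second-surgery result where there is one and the margin otherwise. This stands as a possible reading, so a reader who infers that 4.8.3 overrides 3.3.2 goes further than the text allows. The ambiguity remains because the sentence does not state that reading.

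**The sentence may partly serve another endpoint.** The first SAP 3.4 endpoint is the proportion of positive-margin patients with a LUM signal above threshold. There a positive margin is the right criterion whatever a second surgery shows. This also stands in part. But cancer in a re-excision plays no role in that ratio, and the sentence is placed under the performance evaluation without any limit to 3.4.

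**The scope is narrow.** A reader might infer that LUM cannot be wrong at unshaved sites. The documents do not support that: a LUM-positive site with a clean second surgery and a negative margin is still a false positive, and a LUM-negative site with cancer in the re-excision is still a false negative. The count may be reduced further. Protocol 8.2 makes the image after two shaves optional. Overrides are protocol deviations, which SAP 4.6 sends to adjudication and possible removal from the efficacy analysis, although the SAP does not class them as major.

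**The consequence is limited.** SAP section 1 says the protocol has no pre-defined, hypothesis-tested endpoints, and the illustrated shifts are smaller than the targeted margin of error. Both are true, but a shift that can only favour the device is not excused by being smaller than random error.

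**Conclusion.** The point holds as a conflict on the literal text, limited to one of 12 combinations: LUM-positive, unshaved, positive margin, clean re-excision or mastectomy. There the hierarchy gives a false positive and 4.8.3 can be read as giving a true positive, while the LUM-negative counterpart is a true negative.

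The direction is certain if the literal reading is applied: none of the three accuracy measures can fall. The size is unknown because the documents do not give the number of such orientations, and it is probably small. In the assumed tables, 2 to 10 orientations add about 1 to 3 points to sensitivity and about 0.2 to 3 points to specificity. Only the 51 positives come from the documents. No pass/fail conclusion in this study depends on it. The practical stake is the accuracy carried forward to the pivotal study.

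**What to change.** Replace the sentence in SAP 4.8.3 with wording such as:

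> For sensitivity, specificity and the Youden Index, these orientations are classified by the Section 3.3.2 hierarchy: by re-excision or mastectomy pathology where a second surgery was done, and by the margin only where none was done. The positive-margin criterion applies only to the first Section 3.4 endpoint (LUM signal in positive-margin patients).

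Report the number of LUM-positive, unshaved orientations with a positive margin and a clean second surgery, so that a reader can see how far the choice matters.

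If the sponsor does want either finding to count as truth-positive, the same rule must apply to LUM-negative orientations. The matching LUM-negative case then becomes a false negative, and 3.3.2 has to be amended to say so.

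The cost is about two sentences in the SAP and one reported count. No new data are needed, since second-surgery and margin results are already used elsewhere in the SAP. The downside is that stated accuracy may fall slightly.

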#### 5.4.3 Final margin assessment

Final margin assessment for a given orientation is done on the outermost surface resected for that specific orientation (see **Figure 5**). This surface could be on the main specimen, the SOC shaves or the therapeutic shaves. All the resected tissue will be handled and processed for margin assessment following the institution's current practices for breast conserving surgeries.

LUMICELL CONFIDENTIAL

This document is confidential. Do not disclose or use except as authorized.

**Figure 5:** Final margin assessment for a given orientation is based on the outermost surface resected (marked in red in the sketch). For the example in the sketch, final margin assessment for the medial orientation is based on pathology of the main specimen. Final margin assessments for the lateral orientation is based on the therapeutic shave. Final margin assessment for the superior orientation is based on the selective or comprehensive shave. Final margin assessment for the inferior orientation should be based on the therapeutic shave.

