3.4 Other analyses (secondary endpoints in pivotal study)

This endpoint is defined as:

- Proportion of patients with positive-margins after standard of care breast-conserving surgery who have a LUM Imaging System signal in the cavity above the threshold as defined by the tumor detection algorithm (i.e., a positive LUM signal). The endpoint is estimated as:

$$\frac{\# \text{ positive margin patients after SOC with LUM signal above the threshold}}{\# \text{ positive margin patients after SOC}}$$

- Proportion of subjects with pathology-positive margins after standard of care breast-conserving surgery, for whom additional therapeutic shaves resulted in pathology-negative margins. Note: This efficacy metric also estimates the potential reduction in re-excision surgeries following standard of care breast-conserving surgery that resulted from a positive SOC margin. This is estimated as:

$$\frac{\# \text{ positive margin patients after SOC with all final negative margins after the LUM procedure}}{\# \text{ positive margin patients after SOC}}$$

- Mean absolute volume (cc) of tissue removed from therapeutic shaves. For each subject, absolute shave volume will be calculated as length (c) \times width (c) \times depth (c) for each therapeutic shave with the sum by subject of all therapeutic shaves. Dimensions for the tissue will be obtained as entered in the case report form from the standard of care pathology report. Subjects with no therapeutic shaves taken will have a therapeutic shave volume of 0cc. The proportion of the subjects with and without therapeutic shaves will be reported. The mean and median (with 90% confidence interval) of the total surgery volume of tissue excised and total volume of the SOC tissue will be reported grouped by the subjects with or without therapeutic shaves.

LUMICELL CONFIDENTIAL

This document is confidential. Do not disclose or use except as authorized.

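### SAP 4.8.3 item e excludes therapeutic shaves without a saved image but states no scope; applied literally it conflicts with the final-margin, volume and shave-count definitions

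*SAP*

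**What the plan says.** SAP 4.8.3, item e: "In the case of a therapeutic shave taken but no image saved before the shave was removed, the shave will be excluded from analysis". Nothing else in the item, or elsewhere in the SAP, says which analyses are meant.

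Other rules in the same list do set a scope. Under the Letrozole rule, "the patient will be removed from the device performance evaluation". Item g treats sensitivity and specificity separately from margins: an SOC shave that follows a therapeutic shave in the same orientation leaves the margin evaluation, but stays in the diagnostic one if it has an image.

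The endpoints that item e could touch are defined without reference to a saved image:

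- **Final margin (Protocol 5.4.3):** "Final margin assessment for a given orientation is done on the outermost surface resected for that specific orientation", and "This surface could be on the main specimen, the SOC shaves or the therapeutic shaves".
- **Conversion (SAP 3.4):** among patients with positive margins after standard of care (SOC), the proportion "for whom additional therapeutic shaves resulted in pathology-negative margins".
- **Therapeutic volume (SAP 3.4):** dimensions are multiplied "for each therapeutic shave with the sum by subject of all therapeutic shaves". In addition, "Subjects with no therapeutic shaves taken will have a therapeutic shave volume of 0cc".
- **Volume ratio and shave count (SAP 3.4 c and d):** total resection volume includes therapeutic shaves, and the average count is of shaves taken.

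**The concern.** A missing image removes one thing: the device result that would be set against pathology. It does not undo the resection. The tissue was removed, its outer face may be the patient's final margin, and its volume is part of the tissue cost of the procedure.

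A programmer who applies item e as it stands could delete the shave record before any endpoint is derived. Final margins would then be derived as if that tissue were still in the patient, and the tissue cost of LUM-guided shaving would look smaller than it was. The second-surgery endpoints in SAP 3.4 would still follow the surgery that took place, since SAP 4.8.3 keeps every re-excised patient in the re-excision rates. Margin status and re-excision could therefore disagree for the same patient. SAP 3.4 reads the conversion rate as an estimate of the potential reduction in re-excisions, so that disagreement matters.

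**Working it through.** **1. The plan's own patient number.** Protocol 15.2 needs 32 further pathology positives and cites 19 from 40 Phase B patients. 32 / (19/40) = 67.4, which agrees with the stated figure of approximately 67. It is used below only as a planning size.

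**2. Item e against each endpoint, applied literally.**

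| Endpoint | Is a saved image part of the definition? | Effect of dropping the shave |
|---|---|---|
| Sensitivity, specificity, Youden Index (SAP 3.3) | Yes: the LUM image result is one axis of the 2x2 table | None that is wrong; there is nothing to classify |
| Final margin (Protocol 5.4.3) | No | Misread if the shave was outermost in its orientation |
| Conversion (SAP 3.4) | No | Follows from the misread margin |
| Therapeutic volume and its ratio to total volume (SAP 3.4) | No | Understated |
| Shave count (SAP 3.4 d) | No | Understated |
| Residual-cancer removal (SAP 3.2) | Not stated, but the shave must be LUM-guided | Tumor found in that shave is lost from the numerator |

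**3. Direction of the margin error.** Suppose the SOC margin is positive and an unimaged shave clears it. Without the shave, the margin is read on the inner surface and the patient counts as not converted. Now suppose the inner surface is negative and the unimaged shave has tumor at its outer margin. Without the shave, a positive final margin reads as negative. The error can go either way.

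**4. Leverage of one patient on conversion.** Protocol 3.1 cites close or positive margin rates of 17% to 59%. Applying that range to margins after SOC is an assumption.

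- 67 patients: 67 × 0.17 = 11.4, about 11; 67 × 0.59 = 39.5, about 40. One misread patient moves the rate by 1/11 = 9.1 points to 1/40 = 2.5 points.
- 250 patients (the ceiling in Protocol 15.2): about 42 to 148. One patient moves it by 1/42 = 2.4 points to 1/148 = 0.7 points.

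**5. Leverage on residual-cancer removal.** The denominator is all patients: 1/67 = 1.5 points, or 1/250 = 0.4 points.

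**6. Volume.** If a share f of therapeutic volume comes from unimaged shaves, mean therapeutic volume is understated by f. For the ratio, set main specimen plus SOC volume to 1 and therapeutic volume to T. A true contribution of 20% gives T = 0.20/0.80 = 0.25. With f = 10%, the reported ratio is 0.225/1.225 = 18.4%. Both the 20% and the 10% are assumptions.

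**7. Consistency within the list.** Item j imputes a volume when a shave's dimensions are unknown. Under a literal item e, tissue of unknown size is counted while measured tissue without an image is not.

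**The case against.** The sponsor may have meant only device performance. The paragraph before the list uses nearly the same phrase for retaken and lens-issue images, where only image-based evaluation can be intended, and several neighbouring items refer to device performance. That reading is plausible. However, items g, j and m of the same list deal with margins and volume, so context does not settle the scope. A reader might infer that item e expressly covers every analysis; the text does not say that either. It leaves the scope open.

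A reader might also infer that a patient whose only therapeutic shave lacked an image becomes a 0 cc, no-shave subject and moves to the no-shave arm of the adverse-event comparison. The documents do not support this. SAP 3.4 assigns 0 cc to subjects with no shave taken, and item e itself describes the shave as taken. The adverse-event grouping is a fact about the subject, and item e excludes a shave, not a subject's status.

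Item e does not say which surface replaces the dropped one, and item m sends disagreements between derived and site-reported margin status to adjudication. That may catch some errors. It does not restore the shave to the volume or count endpoints.

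The strongest point concerns credit to the device. Protocol 5.2.2 defines a therapeutic shave by LUM guidance, and without an image that guidance cannot be verified. Crediting such a shave with a conversion is debatable. This stands, and it is why conversion and residual-cancer removal should be shown both ways.

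The stakes are also limited. Protocol 5.4.1 asks for images of all cavity orientations, so an unimaged shave departs from procedure. The SAP introduction states that the protocol has no hypothesis-tested endpoints.

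**Conclusion.** The point holds as an unscoped exclusion rule. It is right for sensitivity, specificity and the Youden Index. Applied literally elsewhere, it contradicts Protocol 5.4.3 and SAP 3.4. The margin effect arises only where the excluded shave was outermost in its orientation, and it has no fixed direction. The volume and count effects run one way, towards understatement.

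The overall bias cannot be sized, because the number of unimaged shaves is not given, and no figure stated in the plan changes. The 9.1 to 2.5 points per misread patient rest on about 67 patients and on the 17% to 59% background rate applying to SOC margins. The volume figures rest on assumed shares. This should be corrected before analysis, but it does not threaten the study as a whole.

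**What to change.** Reword item e to:

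- exclude the shave from sensitivity, specificity and the Youden Index only;
- keep it in final margin status, tissue volumes and shave counts;
- state that the subject counts as having a therapeutic shave, which also settles the 0 cc and adverse-event grouping questions;
- report residual-cancer removal and SOC-positive-to-negative conversion with and without such shaves;
- report how many such shaves there were, and in how many patients.

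The cost is a sentence or two in the SAP and one extra run of two proportions. No new data are needed, because SAP 3.4 already takes tissue dimensions from the case report form.
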